## 8.1. Manufacturer

ProGrip™ Self-Gripping Polyester Mesh is manufactured by Sofradim Production, (wholly owned subsidiary of Medtronic plc.) in Trévoux, France.

## 8.2. Packaging

The device is intended for single use only and is provided in an ethylene oxide sterilized package which includes an expiration date and lot number. A single (1) mesh is contained in each box.

## 8.3. Intended Population

ProGrip™ self-gripping polyester mesh is intended for use in reinforcement of soft tissue where weakness exists, in procedures involving abdominal suture line reinforcement. A thorough assessment of each patient's medical history and conditions shall be performed to determine the suitability for prophylactic mesh augmentation with ProGrip™ self-gripping polyester mesh in the prevention of incisional hernia.

## 8.4. Product Use

Full operating steps are described in the instructions for use (Appendix B, Section 19.2). Briefly,

- The device is designed to be implanted outside of the peritoneal cavity.
- This mesh can be used whole or cut to the required dimensions.
- In case of abdominal suture line reinforcement, the placement of the mesh should ensure necessary overlap of the weakness, according to the surgeon's practice.
- Only a single mesh should be used per subject.

Approximately 135 mesh devices (one per subject) of TMP1509G, TMP1515G, TMP2015G, TMP3015G, TMP1008G, TMP2008G, TMP3008G, or TMP4008G are expected to be used for the study.

## 8.5. Product Training Requirements

Each Investigator participating in the clinical study and the associated clinical study staff will receive training on ProGrip™ self-gripping polyester mesh, if necessary. Investigators and study staff will be trained on device characteristics, shelf life, storage requirements, device use, and warnings, precautions and contraindications.

For investigators who do not know ProGrip™ self-gripping polyester mesh prior to enrolling subjects, they must certify their understanding of the operative technique and anticipated complications associated with the use of this device by completing at least (1) case using the device.

## **8.6. Product Receipt and Tracking**

ProGrip™ self-gripping polyester mesh will be provided to each site upon Sponsor collection and approval of all required regulatory documentation. The ProGrip™ self-gripping polyester mesh will be labeled “For MDT17048POETRY Clinical Investigation”. Device accountability logs and clinical material shipment/return forms will be provided to the site. It is the site’s responsibility to document the receipt (maintain material shipment/return forms), disposition of the product (per subject use, including amount used, amount remaining, etc.), transfer (if applicable) and return of all unopened study devices.

## **8.7. Product Storage**

Once received at the study site, ProGrip™ self-gripping polyester mesh must be stored at room temperature in a secure (locked) location at the study site. Access should be limited to designated study staff only. It is the responsibility of the investigator to correctly handle and store market released product. These products will be used according to their labeling. The investigator shall make sure that all investigational devices will be stored in such a manner as to be easily identifiable. If the investigational device cannot be identified, the device shall not be used.

## **8.8. Product Return**

All unused or expired ProGrip™ self-gripping polyester mesh should be returned to Medtronic within 30 days of the last subject enrolled at the site and it will be documented in the product accountability log and clinical material shipment/return form. If the products are explanted but not returned, a justification will be reported on the appropriate case report forms or disposition logs. To receive a Returned Product Mailer Kit, please contact your local Medtronic field personnel. Additionally, all products involved in a device deficiency and those removed from subjects should be returned to Medtronic as soon as reasonably possible.

## **8.9. Product Accountability**

All products used in this study will be market released in the geographies they are used. Device Traceability may be required per local laws and regulations. If there are additional local requirements related to the ProGrip™ self-gripping polyester mesh beyond what is collected by Medtronic on the CRF, this is the Investigator’s responsibility and should be recorded in the subject’s medical records, but will not be collected by Medtronic (e.g., national registration card number, identification code linked to names and contact information, log of all subjects enrolled in the study, lot or batch number).

Medtronic will perform periodic reconciliation of the investigational product to ensure traceability.

## 9. Study Site Requirements

### 9.1 Investigator / Investigation Study Site Selection

All investigators managing the subject's hernia must be qualified practitioners. All implanting physicians must be experienced and/or trained in the handling of ProGrip™ self-gripping polyester mesh.

The role of the principal investigator is to implement and manage the day-to-day conduct of the clinical investigation as well as ensure data integrity and the rights, safety and well-being of the subjects involved in the clinical investigation.

The principal investigator shall:

- Be qualified by education, training, and experience to assume responsibility for the proper conduct of the clinical investigation
- Be experienced in the field of application and training in the use of ProGrip™ self-gripping polyester mesh
- Disclose potential conflicts of interest, that interfere with the conduct of the clinical investigation or interpretation of results
- Has the ability to comply with the applicable EC and regulatory requirements
- Is not disbarred, disqualified, or working under sanctions in applicable regions
- Be registered at the CNOM
- Be able to demonstrate that the proposed investigational study site:
  - Has adequate time and resources to conduct the study throughout the duration of the study
  - Has access to the required number of eligible subjects needed within the recruitment period
  - Has one or more qualified investigators, a qualified investigational study site team and adequate facilities for the foreseen duration of the clinical investigation
  - Has not had early termination and/or known instances of non-compliance from other clinical studies
  - Adequate study device storage location(s) and processes
  - Acceptable audit or inspection history
  - Acceptable anticipated study startup timeline
  - Lack of potential competition for the same subject population from other ongoing studies

Study site personnel training will be completed and documented prior to participation in this study.

### 9.2 Study Site Activation

During the activation process (prior to subject enrollment), Medtronic will train study site personnel on the clinical investigation plan, on relevant standards and regulations, informed consent, and on data

collection and reporting tools. If new members join the study site team, they will receive training on the applicable study requirements relevant to their role before contributing to the study.

Prior to performing study related activities, all regulatory requirements shall be fulfilled, including, but not limited to the following:

- EC approval (and voting list, as required by local law) of the current version of the CIP and IC.
- RA approval or notification (as required per local law)
- Fully executed CTA
- CV of investigators and key members of the investigation study site team (as required). The signature on the CV must be dated within 3 years prior to the date of activation of the study site.
- Documentation of delegated tasks
- Documentation of study training
- Additional requirements imposed by local regulations, the EC and RA shall be followed, if appropriate.

In addition, all participating study site staff must be trained on the current version of the CIP as well as on the applicable study requirements depending on their role and must be delegated by the principal investigator to perform study related activities.

Medtronic will provide each study site with documentation of study site/investigator readiness; this letter must be received prior to performing study related activities.

### **9.3 Role of the Sponsor Representatives**

Sponsor representatives may provide support at the study site as required for the study under supervision of the Principal Investigator, including:

- Provide study training relevant and pertinent to the involvement of personnel conducting study activities and investigator responsibilities
- Technical support under the supervision of a study investigator, but no data entry, shall be performed by Medtronic personnel or their representatives at study sites
- Monitoring and auditing activities

In addition, for this study, sponsor representatives may be authorized by the Principal Investigator to perform the following significant trial related duties:

- Provide technical support to study investigators performing the study implant procedure

## 10. Selection of Subjects

### 10.1. Study Population

At least 135 subjects undergoing midline laparotomy may be enrolled in up to 12 sites in France using the embedded registry data of Club Hernie. Each site will be allowed to enroll between 1 and 25 subjects. To reduce bias, enrollment will not exceed 25 subjects per site. No randomization, or blinding will take place during the study.

### 10.2. Subject Enrollment

A subject is considered enrolled in the study when it is confirmed they meet all pre-operative inclusion and no exclusion criteria, the ICF is signed and they have been implanted with the device. A subject must be followed for the full 24 months if the procedure was begun or completed with the study device. No study procedures, or data collection will be performed until informed consent form has been completed.

### 10.3. Inclusion Criteria

**Subjects are eligible to be enrolled in the study only if they meet all of the following criteria:**

1. Subject has provided informed consent.
2. Subject is  $\geq 18$  years of age at the time of consent.
3. Subject will be undergoing an elective midline laparotomy.
4. Subject may have a combination of low- and high-risk factors but cannot exceed a total of 5 risk factors or have more than 2 high-risk factors. Subject must have at least 2 low-risk factors if subject does not have any high-risk factors. High- and low-risk factors include:
  - a. High-Risk Factors (maximum of 2):
    - i.  $BMI \geq 35$
    - ii. Prior open abdominal surgery
    - iii. Daily active smoker or Chronic Obstructive Pulmonary Disease (COPD) diagnosis
    - iv. Current or recent (within 1 year) cancer diagnosis or chemotherapy treatment
    - v. History of or current abdominal aorta aneurism or surgery for abdominal aorta aneurism
  - b. Low-Risk Factors (minimum of 2, if no high-risk factors):
    - i.  $25 \leq BMI < 35$
    - ii. Age  $> 45$
    - iii. Uncontrolled diabetes
    - iv. Malnutrition as defined by 10% weight loss within the last 3 months
    - v. Current immunosuppressive treatment
    - vi. Colorectal surgery

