## 10.4. Exclusion Criteria

**Subjects will be excluded from enrollment in the study if they meet any of the following criteria:**

1. Subject is undergoing emergency surgery, i.e. lifesaving procedures performed where subject is in imminent danger of death.
2. Subject for which the device is used outside the product IFU, including:
  - a. Pregnant women: Women who are known or suspected to be pregnant, or who are planning to become pregnant during the study follow-up period
  - b. Subject who has an infection within 30 days of enrollment or, or at the time of the surgery, has any active, acute or chronic infection(s) that are uncontrolled and/or requiring treatment such as antibiotics
  - c. Subject whose surgical site is contaminated or dirty/infected intraoperatively, as assessed by the Investigator (Exclude Altemeier classification III-IV)
3. Subject who had received a mesh in a previous ventral hernia repair or has a ventral hernia.
4. Investigator determined that a planned future surgery would interfere with application of mesh reinforcement.
5. Subject has participated in an investigational drug or device research study within 30 days of enrollment.
6. Subject has a life expectancy of <2 years.
7. Subject has an ASA Physical Status Classification System score >3.
8. Subject has > 5 total risk factors or > 2 high-risk factors.

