## 13.8 Subject Death

All subject deaths must be reported by the investigator to Medtronic on an AE form (AE with outcome of death) as soon as possible after the investigator first learns of the death. In case of death, there should be one AE with the outcome of death.

A copy of the death certificate, if available and allowed by state/local law, should be provided to the Medtronic clinical study team. When a death occurs in a hospital, a copy of the death summary report and all relevant hospital records, if available should be provided to the Medtronic clinical study team. If an autopsy is conducted, a copy of the autopsy report should also be provided to the Medtronic clinical study team if available and allowed by local law. When the death occurs at a remote study site, it is the investigative study site's responsibility to attempt retrieval of information about the death.

In summary, the following data will be collected:

- Date of death
- Detailed description of death
- Cause of death
- Relatedness to system and/or procedure
- Device disposition information
- Death summary/hospital records (if available and allowed by local law)
- Autopsy report (if available and allowed by local law)
- Death certificate (if available and allowed by local law)

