7.9. Evaluation of Objectives

Primary Objective and Endpoint

The primary objective of this investigation is to confirm the efficacy of ProGrip™ Self-gripping Polyester Mesh to reduce the incidence of incisional hernia within 24 months post-operatively in subjects undergoing procedure with midline laparotomies.

The primary endpoint is the incisional hernia rate within 24 months of midline laparotomy assessed by CT-scan and physical examination including hernia clinical examination.

Statistical analysis of primary endpoint will be comparative. Binomial one-way test will be used to compare the observed ProGrip™ Self- gripping Polyester Mesh incisional hernia incidence rate to the 20% theoretical incidence rate (from no prevention population), using a two- sided alpha-level of 5%.

Primary endpoint will be measured using Performance Analysis Set; a confirmatory analysis of primary endpoint will be run using Per Protocol Analysis Set.

Secondary objective and endpoints

The secondary objective of this investigation is to confirm the safety of ProGrip™ Self-gripping Polyester Mesh through the occurrence of adverse device effects or procedure related adverse events following the use of ProGrip™ Self-gripping Polyester Mesh in subjects undergoing procedures with midline laparotomies.

To confirm the safety of ProGrip™ Self-gripping Polyester Mesh through the occurrence of adverse device effects or procedure related adverse events following the use of ProGrip™ Self-gripping Polyester Mesh in subjects undergoing procedures with midline laparotomies.

The following secondary endpoints will be assessed:

- Adverse event (AE) incidence reported by number, severity, seriousness and relationship to the procedure and device from the surgery to the 24-month visit: AE incidence will be measured on Safety Analysis Set.
- Time to incisional hernia occurrence: will be measured using Kaplan Meier estimates, and based on SAS, and PPAS.
- Post-operative pain at the site of surgery: will be measured on SAS and PPAS, at each postoperative timepoint: Day0 (after surgery), Day1, Day8, Day30, Month12 and Month24.
- Quality of life: will be measured on all, PAS, SAS, and PPAS, using Club Hernie QOL questionnaire, combining qualitative and quantitative data, at Month1, Month12 and Month24.
- Patient satisfaction: at 12 then 24 months, measured on PAS, PPAS and SAS
- Surgeon satisfaction, measured on PAS, SAS, and PPAS

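### Time to incisional hernia is estimated by Kaplan-Meier alone with no rule for death as a competing event, so that secondary estimate would overstate 24-month hernia risk to the extent that hernia-free subjects die

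*Protocol*

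**What the plan says.** The method is fixed in one line of SAP 7.9, under the secondary endpoints: "Time to incisional hernia occurrence: will be measured using Kaplan Meier estimates, and based on SAS, and PPAS". In the SAP's abbreviations, SAS is the Safety Analysis Set (all enrolled subjects) and PPAS the Per Protocol Analysis Set. The SAP gives no censoring rule for this endpoint, and neither document mentions competing risks or a cumulative incidence function.

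Protocol 10.3 lists among the high-risk factors that help a subject qualify "Current or recent (within 1 year) cancer diagnosis or chemotherapy treatment" and "History of or current abdominal aorta aneurism or surgery for abdominal aorta aneurism". Protocol 10.4 limits mortality through two exclusions: "Subject has a life expectancy of <2 years" and "Subject has an ASA Physical Status Classification System score >3". ASA 3 is therefore admitted.

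Death is one of the exit reasons in Protocol 11.13.1, and data up to exit are analysed. Protocol 13.8 requires that "All subject deaths must be reported by the investigator to Medtronic on an AE form" and lists the date of death among the items collected.

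The primary analysis is separate. SAP 7.9 states: "The primary endpoint is the incisional hernia rate within 24 months of midline laparotomy assessed by CT-scan and physical examination including hernia clinical examination". It is tested against 20% on the Performance Analysis Set: "Binomial one-way test will be used to compare the observed ProGrip™ Self- gripping Polyester Mesh incisional hernia incidence rate".

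**The concern.** A subject who has died cannot later develop a hernia, so death is a competing event and not a loss of information about a hernia still to come. Plain Kaplan-Meier treats an event-free exit as censoring. It assumes that the censored subject would have gone on to develop hernias at the rate seen in those still followed. One minus Kaplan-Meier then describes a population in which nobody dies. Both documents phrase the study question as the incidence within 24 months in patients undergoing midline laparotomy, which is the share who actually get a hernia. A reader who takes the 24-month height of the curve as that share would read it too high.

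What is at stake is the accuracy of a secondary, descriptive estimate. The study's decision does not depend on it.

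**Working it through.** **1. The plan's own figure, to see whether it is touched.** Inputs from SAP 6 and Protocol 15.6: p0 = 0.20, p1 = 0.10, two-sided alpha 5%, power 80%, attrition 20%.

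n = [1.960 × √(0.20 × 0.80) + 0.842 × √(0.10 × 0.90)]² / (0.10)² = 107.43, rounded up to 108; 108 / 0.80 = 135.

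Both stated figures reproduce. No Kaplan-Meier quantity enters them, so the handling of death in the time-to-hernia curve cannot change them.

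**2. Size of the overstatement, starting from a true incidence of 10%.** Let h be the proportion with a hernia by 24 months, set to the planning value 0.10. Let d be the proportion who die hernia-free by then. The documents give no value for d, so it is varied. With constant cause-specific hazards and no other losses:

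- total cumulative hazard H = −ln(1 − h − d)
- hernia part = H × h / (h + d)
- one minus Kaplan-Meier = 1 − exp(−hernia part)

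| d (assumed) | H | Hernia part | One minus KM | Excess over 10% (points) |
|---|---|---|---|---|
| 5% | 0.1625 | 0.1083 | 10.27% | 0.27 |
| 10% | 0.2231 | 0.1116 | 10.56% | 0.56 |
| 15% | 0.2877 | 0.1151 | 10.87% | 0.87 |
| 20% | 0.3567 | 0.1189 | 11.21% | 1.21 |

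**3. The same check from the other end.** Fix one minus Kaplan-Meier at 10%, and let D be the 24-month probability of death if hernia did not intervene. With a = −ln(0.90) and b = −ln(1 − D), cumulative incidence = a / (a + b) × [1 − exp(−(a + b))].

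| D (assumed) | Cumulative incidence | Kaplan-Meier excess (points) |
|---|---|---|
| 2% | 9.90% | 0.10 |
| 5% | 9.75% | 0.25 |
| 10% | 9.50% | 0.50 |
| 15% | 9.24% | 0.76 |
| 20% | 8.98% | 1.02 |

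At D = 20% the excess is 135 × 0.0102 ≈ 1.4 subjects.

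**4. Detection only at the 12- and 24-month visits.** Split each risk equally over the two years: h′ = 1 − √0.90 and d′ = 1 − √(1 − D), with death before the visit preventing detection. Cumulative incidence = (1 − d′)h′ + (1 − d′)²(1 − h′)h′. For D = 20%, h′ = 0.0513 and d′ = 0.1056, giving 8.48%, an excess of 1.52 points. For D = 2% the excess is 0.15 points.

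**5. Against sampling error.** At 10% with n = 135, the 95% half-width is about 1.96 × √(0.10 × 0.90 / 135) = 5.1 points. Every excess above is well inside it.

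**The case against.** The case for leaving the plan alone has real strength:

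- Time to hernia is secondary and descriptive, and the SAP nowhere says that one minus Kaplan-Meier at 24 months will be presented as the incidence.
- Censoring at death is the default of the method, not a written rule.
- The exclusions for short life expectancy and ASA above 3 hold mortality down. Reaching 20% deaths would use up all the planned attrition.
- The bias is small against the confidence interval and makes the mesh look worse, so it cannot produce a false efficacy claim.
- Censoring deaths is also a recognised choice if the aim is to describe hernia risk among survivors.

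All of this limits the weight of the point. It does not remove it. A prognosis judged at baseline lowers mortality but does not make it zero, and a plan that means to describe risk among survivors should say so.

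Two stronger readings should be resisted. A reader might infer that the study's headline 24-month incidence is overstated. It is not: that figure is a binomial proportion and makes no use of Kaplan-Meier.

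A reader might also infer that deaths would push the curve away from the primary proportion and that the remedy would bring the two together. The documents do not say whether hernia-free deaths stay in the primary denominator. With 10% hernias and 5% deaths, the proportion is 10.0% if they stay and 10/95 = 10.5% if they are dropped; Kaplan-Meier reads 10.3% and Aalen-Johansen 10.0%. With 20% deaths dropped, it is 10/80 = 12.5%, against 11.2% and 10.0%. On that reading, Kaplan-Meier lies nearer the primary result, so agreement with it is no argument for the change.

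**Conclusion.** The point holds as a minor, conditional one about SAP 7.9. The direction is certain if hernia-free deaths are censored and the curve is read as actual risk. The size depends on mortality, which the documents do not give: about 0.3 to 1.2 points at a true 10% incidence for 5% to 20% deaths under constant hazards, and up to about 1.5 points in the visit-only model. At 10% deaths or fewer it is below one point in every calculation shown. The inclusion criteria contain no error; they matter only because they make some deaths foreseeable.

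**What to change.** In SAP 7.9, define the estimate for time to incisional hernia as the cumulative incidence function (Aalen-Johansen) with death as a competing event. Report the 24-month value with its 95% CI on the sets already named, and keep the Kaplan-Meier curve as a supportive display labelled as censoring deaths. State the censoring rule for other exits in the same paragraph.

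The cost is SAP wording and one extra standard analysis. Dates of death are already collected under Protocol 13.8, which covers all deaths and not only device- or procedure-related ones. The eligibility criteria, the primary test and the sample size stay as they are.
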